### **3. List of Abbreviations:**

Visual Analog Scale (VAS)

Neck Disability Index (NDI)

Hospital Anxiety and Depression Scale (HADS)

Work Limitations Questionnaire (WLQ)

the Modified Brügger's Exercise (MBE)

the Modified Proprioceptive Neuromuscular Facilitation Diagonal Flexion Exercise (MPNDFE)

### **5. Research Synopsis**

#### **Study Title**

Effects of Online Exercise Intervention on Physical and Mental Conditions in Young Adults with Chronic Neck Pain

#### **Study Population**

The target participants were adults with self-reported non-specific neck pain for more than three months. They were recruited through posters and social media in the campus of the Beijing Sport University.

#### **Study Design**

The present study was an assessor blinded randomized controlled trial conducted according to the Declaration of Helsinki (World Medical Association, 2013). The Institutional Review Board of the Beijing Sport University approved the study (reference number: 2023006H).

#### **Sample Size**

With an anticipated dropout rate of 15%, a total of 39 participants was required.

#### **Study Duration**

Totally 8 weeks, including 1-week baseline testing, 6-week intervention and 1-week post intervention testing.

### **Study Intervention Description**

Participants in both groups completed the same exercise program three times a week for six weeks with either face-to-face or online mode of delivery by physiotherapists.

### **Primary Objective**

The primary objective is to study the effectiveness of online and conventional exercise therapy on pain level and function in adults with chronic neck pain. There were three primary outcomes, including average and maximum neck pain using visual analog scale (VAS), and Neck Disability Index (NDI).

### **Secondary Objectives**

The secondary objectives are investigating the effectiveness of online and conventional exercise therapy on mental condition and working efficacy in adults with chronic neck pain. There were two secondary outcomes: anxiety and depression measured with the Hospital Anxiety and Depression Scale (HADS) and work efficiency assessed with the Work Limitations Questionnaire (WLQ).

## **6. Background and Significance:**

Neck pain is one of the most common musculoskeletal disorders causing significant burden in public health worldwide (Safiri et al., 2020). In China, neck pain also influences large population, the age standardized point prevalence of neck pain was 4532.6 per 100000 persons, which was higher than the global age standardized point prevalence of 3551.1 per 100000 persons in 2017 (Safiri et al., 2020; Wu et al., 2021). The China Mental Health Survey reported that the prevalence of chronic back or neck pain among people with any mental disorders was more than twice that of those without mental disorder (Xu et al., 2020). It is believed that psychological factors such as stress, distress, anxiety, mood and emotions, cognitive function and pain-related behaviors are important factors related to chronic neck pain (Kazeminasab et al., 2022). Additionally, because of COVID-19 pandemic, people's physical activity has been greatly reduced and the prevalence of anxiety and depression all over the world is prone to increase. In 2020, the pandemic will lead to an increase of 27.6% in cases of severe depression and 25.6% in cases of anxiety disorders worldwide (Santomauro et al. 2021). In this way, people with chronic neck pain may have a higher risk to develop mental disorder.

Most chronic neck pain is non-specific with no identifiable pathoanatomical cause (Beltran-Alacreu et al., 2018). Many therapies have been used to treat patients with chronic non-specific neck pain but exercise therapy is considered as the integral component of interventions (Blanpied et al., 2017). It has also been proved that exercise can reduce the symptoms of depression, anxiety and pain in patients with neck pain (Nazari et al., 2018). However, due to the lack of time, money and rehabilitation resources, many people cannot receive high quality conventional rehabilitation. Since the start of COVID-19 pandemic in 2020, it became more difficult to deliver the conventional form of exercise therapy to those patients with chronic neck pain by the physiotherapists. In response to this crisis, telerehabilitation, as a new service mode of delivering rehabilitation, has become popular for physiotherapists to treat various musculoskeletal, neurological and cardiopulmonary disorders (Havran and Bidelsbach, 2021). Telerehabilitation not only alleviates the time cost and economic cost of patients, but also reduces the pressure on the medical system (De Biase et al., 2020). In addition, online rehabilitation can maximize the use of high-quality rehabilitation resources, and neck pain patients in remote areas can also receive the cutting-edge and effective interventions at home. Recent review on systematic reviews of telerehabilitation in physiotherapy provides preliminary evidence that “telerehabilitation in physical therapy could be comparable with in-person rehabilitation or better than no rehabilitation for conditions such as osteoarthritis, low-back pain, hip and knee replacement, and multiple sclerosis and also in the context of cardiac and pulmonary rehabilitation” (Seron et al., 2021). However, the efficacy of telerehabilitation for patients with chronic non-specific neck pain is still unknown. A Cochrane review protocol on telerehabilitation for neck pain has been published but the review results are not available yet (Fandim et al., 2021).

## 7. Objectives:

People with chronic neck pain suffer from persistent pain with impaired physical function and mental health. The proportion of mental issues among them is much higher than healthy population. The purposes of this study were to compare the efficacy of online exercise therapy with conventional exercise therapy on pain, function, psychological status and work efficiency of young adults with chronic neck pain.

Objective outcome assessments were taken at baseline prior to randomization and after the 6-week intervention period. Additional assessments of the Work Limitations Questionnaire were done after two weeks and four weeks of intervention.

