### **Secondary Objectives**

The secondary objective is to investigate the effectiveness of online and conventional exercise therapy on mental condition and working efficacy in adults with chronic neck pain. There were two secondary outcomes: anxiety and depression measured with the Hospital Anxiety and Depression Scale (HADS), and work efficiency assessed with the Work Limitations Questionnaire (WLQ).

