## **8. Study design/methodology:**

Randomized clinical trial with 39 adults with self-reported chronic neck pain recruited. They were randomly assigned into two groups. The experimental group received online exercise therapy and the control group received conventional exercise therapy.

Participants in both groups completed the same exercise program three times a week for six weeks with either face-to-face or online mode of delivery by physiotherapists. The degree of pain was assessed by the improvement in average and maximum visual analogue scale (VAS). Neck function and work limitations were assessed by the Neck Disability Index (NDI) and Work Limitations Questionnaire (WLQ) respectively. The Hospital Anxiety and Depression Scale (HADS) and its subscales were used to evaluate anxiety and depressive symptoms. Participants were assessed at baseline and at 6 weeks while the changes in WLQ were assessed biweekly. To ensure the effectiveness of online exercise therapy, therapists delivered the online exercise 3 times a week for 6 weeks, with videoconferencing once a week and posting of exercise record on WeChat app twice a week.

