### **13. Statistical Analysis Plan:**

Continuous data were expressed as means and standard deviations. Categorical data were shown as frequencies or percentages. All statistical analyses were conducted using the IBM SPSS Statistics for Windows, Version 24.0 (Armonk, NY: IBM Corp). The normality of continuous data was checked with the Shapiro-Wilk test. The change scores of the primary and secondary outcome variables from baseline to end of intervention between the two groups were compared using independent sample t test. Within-group comparisons were done using paired sample t test. The level of significance of all statistical tests was set with two-tailed at 0.05. Per-protocol analysis was used. The sample size for the study was calculated to be 32 using the G\*Power 3.1.9.2 (Universitat Kiel, Germany), with an estimated effect size of group difference of 0.9 in primary outcomes and a level of significance of 0.05, statistical power of 80% with two-tailed independent sample t test. The estimated effect size was based on previous studies of home exercise on patients with neck pain (Zronek et al., 2016). With an anticipated dropout rate of 15%, a total of 39 participants was required.

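### Week-2 and week-4 WLQ scores are collected but given no stated inferential use; one mixed model on all randomised participants would be a cheap improvement over the planned per-protocol change-score t test

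*Combined protocol and SAP*

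**What the plan says.** Section 7 of the combined protocol and SAP sets outcome assessment at baseline and after the 6-week intervention, then adds: "Additional assessments of the Work Limitations Questionnaire were done after two weeks and four weeks of intervention". Section 8 agrees: "Participants were assessed at baseline and at 6 weeks while the changes in WLQ were assessed biweekly". WLQ is therefore measured four times (weeks 0, 2, 4 and 6). It is one of two secondary outcomes, and the only outcome with interim visits.

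Section 13 gives all outcomes the same treatment. "The change scores of the primary and secondary outcome variables from baseline to end of intervention between the two groups" are compared by independent t test, with paired t tests within groups. On the analysis set it says only "Per-protocol analysis was used". It does not define that set, name a repeated-measures model or a missing-data method, or say what the week-2 and week-4 scores are for. It anticipates 15% dropout among 39 participants.

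**The concern.** A change score from baseline to week 6 exists only for people with a week-6 score. With no missing-data method, someone who leaves after week 4 contributes nothing to the WLQ comparison, although three of their four scores are on file.

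Two things are at stake. The first is precision: the planned test neither adjusts for baseline nor uses the interim visits. The second is possible bias. The arms differ in contact. Under section 10 the control group attends three laboratory sessions a week, while the online group has one video meeting and does the other two sessions alone. Dropout for different reasons in the two arms is plausible, though not documented. If it relates to how WLQ is changing, a completer comparison is biased, and the interim scores are the data that could correct it.

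**Working it through.** **Inputs from the documents.** N = 39, 15% dropout, WLQ at weeks 0, 2, 4 and 6, baseline-to-end t test, per-protocol set. There is no WLQ figure in the plan to reproduce; the sample size rests on the primary outcomes. (From section 13's two-tailed inputs a t test needs 21 per group, 42 in all, not 32. That is a separate matter and does not enter here.)

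**Assumptions.** The documents give no WLQ standard deviation, correlation, allocation ratio or dropout pattern. I take 19.5 per arm, SD = 1, and correlations either AR(1) 0.7 to 0.9 between adjacent visits or exchangeable 0.5 to 0.7.

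**Who is affected.** 39 × 0.15 = 5.85 dropouts. At 5% per interval, 39 × 0.05 ≈ 2 leave before week 2 (no post-baseline score), 2 between weeks 2 and 4, and 2 between weeks 4 and 6.

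**Precision.** Let ρ be the baseline to week-6 correlation. Per completer, the change score has variance 2(1 − ρ); the baseline-adjusted score has 1 − ρ². Their ratio is (1 + ρ)/2, ignoring the small cost of estimating the slope. The all-visit figure is the generalised least squares variance of the week-6 contrast, with a common baseline mean and 5% dropout per interval.

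| Correlation | ρ | Baseline-adjusted ÷ change score | All visits ÷ change score | All visits ÷ baseline-adjusted |
|---|---|---|---|---|
| AR(1) 0.7 | 0.7³ = 0.343 | 0.67 | 0.65 | 0.970 |
| AR(1) 0.9 | 0.9³ = 0.729 | 0.86 | 0.82 | 0.954 |
| Exchangeable 0.5 | 0.5 | 0.75 | 0.74 | 0.985 |
| Exchangeable 0.7 | 0.7 | 0.85 | 0.83 | 0.978 |

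The total variance reduction is 17% to 35%. The last column is what the interim visits add: 1.5% to about 5%.

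**Bias when dropout follows interim worsening.** Suppose the fraction q with the highest score on (week 4 − baseline + noise of equal variance) leaves after week 4. The completers' mean change shifts by C/S × φ(z)/(1 − q), where C = 1 + r(4,6) − r(0,6) − r(0,4), S = √[4(1 − r(0,4))] and z is the upper q point of the standard normal.

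- Exchangeable 0.7: C = 0.3, S = √1.2 = 1.095, C/S = 0.274.
- AR(1) 0.7: C = 1 + 0.7 − 0.343 − 0.49 = 0.867, S = √2.04 = 1.428, C/S = 0.607.
- 15% in one arm, none in the other: φ/(1 − q) = 0.233/0.85 = 0.274. Bias is 0.274 × 0.274 = 0.08 to 0.607 × 0.274 = 0.17 SD. Without the noise term, multiply by √2: 0.11 to 0.24 SD.
- 20% v 10%: 0.280/0.80 − 0.1755/0.90 = 0.350 − 0.195 = 0.155. Bias is 0.04 to 0.09 SD, about 0.16 to 0.25 of the completer standard error.
- The same rate and mechanism in both arms: the shifts cancel and the bias is zero.

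Baseline adjustment among completers alone still leaves 0.05 to 0.11 SD in the one-arm 15% case.

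**Other mechanisms.** A simulation with 20 and 19 participants, 6,000 runs per scenario, true difference zero and correlations of exchangeable 0.5, exchangeable 0.7 or AR(1) 0.8 compared the completer change score with the likelihood estimate from all four visits. That estimate used separate baseline means by arm.

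| Dropout depends on | Completer bias (SD) | All-visit bias (SD) |
|---|---|---|
| Nothing (random) | about 0 | about 0 |
| Interim change, both arms alike | about 0 | about 0 |
| Interim level, one arm only | within 0.01 | within 0.01 |
| Interim change, one arm only | −0.06 to −0.21 | within 0.01 |
| Unseen week-6 value, one arm only | −0.04 to −0.07 | −0.05 to −0.09 |

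Only the fourth row shows a bias that the interim scores remove.

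**The case against.** A reader might infer that using the interim scores would reduce dropout bias. The documents do not support that. They give 15% overall, with no pattern or imbalance by arm. Of the five mechanisms above, three leave no bias to remove and one is not improved. The near-zero result in the fourth row also follows by construction, because dropout was generated from scores the model uses. This objection stands: the right word is could.

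A reader might also credit the interim visits with the 17% to 35% precision gain. Most of it needs only baseline adjustment. Likewise, moving from per-protocol to all randomised participants is a separate change: someone excluded for non-adherence who has a week-6 score needs only the wider set.

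Nor is the change free. An unstructured covariance for four visits has 4 × 5/2 = 10 parameters, estimated from 39 people, and the model relies on missing at random.

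Finally, it goes too far to say that the interim scores have no planned use at all. Section 13 summarises continuous data by means and standard deviations without limiting the visits. It also fixes one between-group interval, so fear of a t test at every visit is hypothetical. What survives is narrower: no inferential use is stated, and participants without week 6 are dropped.

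**Conclusion.** The point holds as a cheap improvement to one secondary analysis, not as an error that invalidates it. Followed exactly, section 13 discards every WLQ score from participants without a week-6 value and makes no baseline adjustment.

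The size rests wholly on assumed correlations and dropout patterns. The completer bias range includes zero, and its upper figures need dropout tied to interim worsening mainly or only in one arm. Likelihood methods remove such bias only if dropout depends on observed scores; those who leave before week 2 supply only a baseline. The case for the interim visits is therefore mainly protection against one plausible form of dropout, with a small gain in precision.

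Nothing here bears on the primary outcomes or HADS, which have no interim visits.

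**What to change.** In section 13, replace the WLQ change-score t test with one linear mixed model:

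- **Population:** all randomised participants with any WLQ score. Kept inside a per-protocol set, the model would not recover the people it is meant to include.
- **Mean structure:** categorical week, arm-by-week terms, and a baseline mean common to both arms.
- **Covariance:** unstructured, with a named small-sample degrees-of-freedom correction and a simpler fallback structure stated in advance in case of non-convergence. Confirm that the named software version offers the chosen correction.
- **Inference:** the week-6 arm difference is the single WLQ test; weeks 2 and 4 are descriptive.
- **Assumption:** state that the analysis assumes missing at random, and report dropout by arm and by interval so that readers can judge it.

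The cost is a paragraph of SAP wording and one model. No new data are needed. The price is a stated missing-data assumption and more parameters to estimate from 39 people. If the planned analysis has already been run, report both and say which came first.

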### Primary Objective

The primary objective is to investigate the effectiveness of online and conventional exercise therapy on pain and function in adults with chronic neck pain. One primary outcome was the average and maximum neck pain measured by visual analog scale (VAS). Another outcome was the neck dysfunction measured by the Neck Disability Index (NDI).

### **Secondary Objectives**

The secondary objective is to investigate the effectiveness of online and conventional exercise therapy on mental condition and working efficacy in adults with chronic neck pain. There were two secondary outcomes: anxiety and depression measured with the Hospital Anxiety and Depression Scale (HADS), and work efficiency assessed with the Work Limitations Questionnaire (WLQ).

## **8. Study design/methodology:**

Randomized clinical trial with 39 adults with self-reported chronic neck pain recruited. They were randomly assigned into two groups. The experimental group received online exercise therapy and the control group received conventional exercise therapy.

Participants in both groups completed the same exercise program three times a week for six weeks with either face-to-face or online mode of delivery by physiotherapists. The degree of pain was assessed by the improvement in average and maximum visual analogue scale (VAS). Neck function and work limitations were assessed by the Neck Disability Index (NDI) and Work Limitations Questionnaire (WLQ) respectively. The Hospital Anxiety and Depression Scale (HADS) and its subscales were used to evaluate anxiety and depressive symptoms. Participants were assessed at baseline and at 6 weeks while the changes in WLQ were assessed biweekly. To ensure the effectiveness of online exercise therapy, therapists delivered the online exercise 3 times a week for 6 weeks, with videoconferencing once a week and posting of exercise record on WeChat app twice a week.

## **9. Study Population:**

The target participants were adults with self-reported non-specific neck pain for more than three months. They were recruited through posters and social media in the campus of the Beijing Sport University.

### **Inclusion /Exclusion Criteria**

The inclusion criteria were: (1) adults between 18 and 50 years of age with neck pain (from occiput

to 7th cervical vertebra) for at least 3 months; (2) a score of  $\geq 4/50$  on the Neck Disability Index. Those participants with the following were excluded: (1) adults with a history of previous neck surgery, cervical radiculopathy, acute neck injury or fracture; (2) persons who had more than two hours of moderate intensity exercise or more than four hours of low intensity exercise in a week; and (3) persons who had received any form of physiotherapy treatment in the last 6 months.

## **10. Interventions:**

Participants in both groups completed the same exercise program three times a week for six weeks with either face-to-face or online mode of delivery by physiotherapists.

At baseline, the suitable elastic bands (Thera-band®) for performing the exercises were selected by testing the 15 repetitions maximum (15RM) of the Modified Brügger's Exercise (MBE) and the Modified Proprioceptive Neuromuscular Facilitation Diagonal Flexion Exercise (MPNFDDE) for the participants of both the experimental group and control group. The details of the MBE and MPNFDDE were described in supplementary file 1.

Participants randomized to the control group performed the following exercises three times a week for six weeks in a group of 3-5 participants in the laboratory of the Sport Medicine and Rehabilitation School of the Beijing Sport University:

- A. Warm-up exercises
- B. Cranio-cervical flexion exercises
- C. Strength-endurance exercises
- D. Scapular stabilization exercises
- E. Stretching exercises

[figure not shown]
The details of the exercises were described in supplementary file 2.

Participants allocated to the experimental group performed the same set of exercise three times a week for six weeks in their home, with the following arrangements:

The participants had weekly online exercise meetings with the physiotherapist in a group of 3-5 participants using the TENCENT Meeting. Then the participants performed the remaining two sessions of exercises themselves weekly. If they had encountered any problems, they could consult the physiotherapist during the online session or texting to the physiotherapist using the WeChat app. All the participants of the experimental group received a package of exercise pamphlet and a video disc containing 17-minute exercise demonstrations by the physiotherapist.

## 11. Study Schedule:

CONSORT 2010 Flow Diagram

## 12. Adverse Event Reporting:

In this study, the tests and interventions may include physical activities, which may irritate neck pain and have little risk of heart attack and other life-threatening conditions. During the test and trial, if there are adverse reactions such as acute aggravation of neck pain, the test or intervention will be stopped immediately, and emergency treatment will be conducted. If there is any emergency, the principal investigator(s) will provide basic life support including chest compressions and ventilation until emergency medical staff are on hand. Participant can consult the general practitioners if they

are experiencing any side effects from taking part in the study and should also inform the Principal Investigator.

### **13. Statistical Analysis Plan:**

Continuous data were expressed as means and standard deviations. Categorical data were shown as frequencies or percentages. All statistical analyses were conducted using the IBM SPSS Statistics for Windows, Version 24.0 (Armonk, NY: IBM Corp). The normality of continuous data was checked with the Shapiro-Wilk test. The change scores of the primary and secondary outcome variables from baseline to end of intervention between the two groups were compared using independent sample t test. Within-group comparisons were done using paired sample t test. The level of significance of all statistical tests was set with two-tailed at 0.05. Per-protocol analysis was used. The sample size for the study was calculated to be 32 using the G\*Power 3.1.9.2 (Universitat Kiel, Germany), with an estimated effect size of group difference of 0.9 in primary outcomes and a level of significance of 0.05, statistical power of 80% with two-tailed independent sample t test. The estimated effect size was based on previous studies of home exercise on patients with neck pain (Zronek et al., 2016). With an anticipated dropout rate of 15%, a total of 39 participants was required.

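### The planned t test on change scores is valid but usually less precise than ANCOVA on the baseline score already collected, in a trial sized for 32 analysed participants

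*Combined protocol and SAP*

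**What the plan says.** Section 13 (Statistical Analysis Plan) sets the between-group comparison. Its subject is "The change scores of the primary and secondary outcome variables", and these "from baseline to end of intervention between the two groups were compared using independent sample t test". The measures covered are average VAS, maximum VAS and NDI (primary) and HADS and WLQ (secondary). No ANCOVA, regression model or baseline covariate appears in Section 13 or elsewhere in the document.

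The baseline values exist and were taken before allocation. Section 7 states: "Objective outcome assessments were taken at baseline prior to randomization and after the 6-week intervention period". Section 8 confirms the randomized design: "They were randomly assigned into two groups".

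The trial was sized "with an estimated effect size of group difference of 0.9 in primary outcomes", with "statistical power of 80% with two-tailed independent sample t test". This gave 32 participants, raised to 39 for 15% dropout. Section 13 does not say whether the 0.9 is in SDs of the change or of the raw score. It also states: "Per-protocol analysis was used".

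**The concern.** A change score does use the baseline, but it subtracts the whole of it, which fixes the slope of the week-6 score on baseline at 1. ANCOVA estimates that slope from the data. The true slope is r × SD(week 6)/SD(baseline), which is below 1 whenever the SDs are similar and r is below 1. The change score then over-corrects a chance baseline difference: an arm that happens to start with more pain looks as if it improved more than delivery mode explains.

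Under randomization this averages out over repeated trials, so the test is not biased. What is at stake is precision. Section 7 gives the purpose as comparing online with conventional delivery, so the between-group difference and its confidence interval carry the conclusion. With about 32 people analysed there is little precision to spare, and the covariate that could recover some has already been measured.

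**Working it through.** **Inputs.** From Section 13: effect size 0.9, two-sided alpha 0.05, 80% power, 32 before dropout, 39 recruited. Assumed, because the documents do not give them: 1:1 allocation, the correlation r, and k = SD(week 6)/SD(baseline). Baseline SD is set to 1.

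**1. The plan's own figure.** With d = 0.9, two-sided alpha 0.05 and a t test, 80% power needs 21 per arm, 42 in total (power 81.2%). The stated 32 matches a one-sided test (16 per arm, 80.03%). Two-sided power at 16 per arm is 69.3%. This sizing discrepancy is a separate matter; it explains why the t test stands at 69% rather than 80% below.

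**2. Variances.**
- Change score: k² + 1 − 2rk.
- ANCOVA: k²(1 − r²), times 1 + 1/(N − 4) for estimating the slope. At N = 32 that factor is 1 + 1/28 = 1.036.
- Before the small-sample factor, the change-score variance exceeds the ANCOVA variance by (1 − rk)², which is never negative. ANCOVA can therefore lose at most 1/28, about 4% in variance.
- With k = 1 the ratio ANCOVA/change score is (1 + r)/2 before the factor. Example at r = 0.5: 0.75 × 1.036 = 0.78, and √0.777 = 0.88, an interval about 12% narrower.

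**3. Equal SDs, 16 per arm.** Power takes 0.9 in change-score SDs.

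| r (assumed) | (1 + r)/2 | with factor | CI narrower by | t test power | ANCOVA power |
|---|---|---|---|---|---|
| 0.3 | 0.65 | 0.67 | 18% | 69% | 85% |
| 0.5 | 0.75 | 0.78 | 12% | 69% | 80% |
| 0.7 | 0.85 | 0.88 | 6% | 69% | 75% |
| 0.8 | 0.90 | 0.93 | 3% | 69% | 72% |
| 0.9 | 0.95 | 0.98 | 1% | 69% | 70% |

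Break-even is (1 + r)/2 × 29/28 = 1, so r = 0.93. At r = 0.95 the ratio is 1.01.

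The t test power is the noncentral t with noncentrality 0.9 × √(16 × 16/32) = 2.55 and 30 df. For ANCOVA, 0.9 is divided by the square root of the ratio with factor, with 29 df. Simulation of normal data (200,000 trials per setting) gives the same rounded powers. In a further simulation with no treatment effect (20,000 trials per setting), type I error was 0.050 to 0.054 for the t test and 0.049 to 0.051 for ANCOVA, so both are valid.

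**4. Other readings.**
- All 39 analysed (19/20), 0.9 in change-score SDs: t test 78%; ANCOVA 92%, 88%, 83%, 81% and 79% at r = 0.3, 0.5, 0.7, 0.8 and 0.9.
- 0.9 in raw SDs, 16 per arm: 55% against 72%, 69% against 80%, 89% against 92%, and 97% against 98% at r = 0.3, 0.5, 0.7 and 0.8.

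**5. Unequal SDs, N = 32, factor included.**
- k = 0.8: ratio 0.52, 0.59 and 0.65 at r = 0.3, 0.5 and 0.7.
- k = 1.2: 0.79, 0.90 and 1.00 at the same r. At r = 0.8 it is 1.44 × 0.36 × 1.036/0.52 = 1.03, a small loss.
- k = 1.4, r = 0.7: 1.04, also a small loss.

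**6. Chance baseline imbalance.** The standard error of the baseline difference at 16 per arm is √(2/16) = 0.354 SD. With equal SDs, the change-score estimate is off by (1 − r) times the imbalance. For a one-standard-error imbalance that is 0.25, 0.18, 0.11 and 0.07 SD at r = 0.3, 0.5, 0.7 and 0.8. An effect of 0.9 change-score SDs is 0.9 × √(2(1 − r)) raw SDs, so these errors are 23%, 20%, 15% and 12% of it. The probability of an imbalance above 0.3 SD in either direction is 40% at 16/16 and 35% at 19/20, so it is less likely than not.

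**The case against.** The plan is coherent as it stands: the change-score t test is a legitimate analysis and the same kind of test was used for sizing. The gain cannot be fixed from the documents, since r and the SDs are unknown and three primary outcomes may have three different correlations. At r of 0.8 or above it is small, and with a week-6 SD well above the baseline SD it can become a slight loss. The 69% power reflects a sample size that does not follow from the stated two-tailed inputs. The per-protocol set can bias either method, so calling the test valid needs care. And Section 13 is written in the past tense, so the analysis may already have been run.

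Most of this stands as a limit on size, not as a reason to leave the plan alone. The unknown r is why a range is shown. The possible loss is capped at about 4% in variance, whereas the possible gain is several times larger. The 69% should not be laid at the door of the change score; only the difference between the two power columns belongs to this point. Validity here means the estimator under randomization, and the per-protocol exclusions affect both methods. If the analysis is already done, ANCOVA can only be supplementary, which lowers its value but does not remove it.

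**Conclusion.** The point holds as an efficiency improvement that should be made, not as an error. With equal SDs and 32 analysed, ANCOVA gains precision for any r below about 0.93. The gain is useful at low to moderate r (interval 18% narrower at 0.3, 12% at 0.5) and small at 0.8 or above (3% or less). It disappears when the week-6-on-baseline slope is near 1, for example at r = 0.7 with an SD ratio of 1.2. These figures rest on assumed correlations and SD ratios, 1:1 allocation and normal data; the power figures also depend on which SD the 0.9 refers to. Confidence in the size of the gain is therefore moderate.

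**What to change.** In Section 13, make ANCOVA the between-group analysis for average VAS, maximum VAS and NDI: week-6 score as outcome, group as factor, baseline score of the same measure as covariate. Report the adjusted difference with its 95% confidence interval. Use the same model for HADS and week-6 WLQ. A repeated-measures model for WLQ that uses weeks 2 and 4 is optional; if used, it should include baseline-by-visit and group-by-visit terms and an unstructured covariance.

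If outcome data have already been analysed, keep the planned t test, report ANCOVA beside it, and label it as added after the plan.

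The cost is one sentence in the SAP and one degree of freedom per model, with no new data. After the fact, it is one extra model per outcome.
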